9.3.2 Efficacy Analyses

The primary efficacy endpoint will be analyzed using a repeated measures analysis of covariance on percent change-from-baseline variable to compare the time profile between treatments where

the visit will be the time factor (up to Week 16); and the stratification factor PGA score, treatment group, and interaction term for treatment-by-visit will be the fixed effects and the baseline value will be the covariate. An unstructured variance-covariance matrix will be used. Additional interaction terms will also be included in supportive statistical models and will be detailed in the SAP.

A similar approach as for the primary endpoint will be done for all other continuous efficacy endpoints.

For categorical efficacy endpoints involving proportions of PGA (e.g. the proportion of subjects achieving at least a 2-grade reduction from baseline to clear (0) or almost clear (1) in PGA at week 16), a Cochran Mantel Hansel test (CMH) controlling for PGA at baseline will be performed.

Overall type I error control

For the primary endpoint of percent change-from-baseline in hand mTLSS at Week 16, a Holm's step-down procedure (1979)¹⁴ adjustment will be done to test the two comparisons of interest (40mg vs. Placebo and 80mg vs. Placebo).

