3 STUDY DESIGN

3.1 Overall Design

This study will be performed at approximately 20-25 study centers located in the United States and Canada.

Approximately 105 subjects with moderate to severe CHE (as defined by a hand PGA = 3 or 4 at Day 1) will be included in this randomized, double-blind, placebo-controlled, multicenter, Phase 2 study. Subjects will be men or women, 18 years of age or older, at the time of consent. Subjects with moderate CHE will be limited to 30% of total enrollment.

Each subject should read and sign an informed consent form prior to any screening procedures being performed. Subjects who fulfill all of the inclusion criteria and none of the exclusion criteria will be accepted into the study. After a screening period of no more than 30 days (from Day -30

PPD	STATISTICAL ANALYSIS PLAN, Version Final 1.0
Protocol Number: ASN002AD-202 V6.0	Sponsor: Asana BioSciences, LLC

to Day -1), eligible subjects will be randomized (1:1:1) on Day 1 to receive ASN002 at 40 mg or 80 mg, or placebo once daily for 16 weeks (Part A). Randomization will be stratified for the biopsy collection and for the PGA score of '3' (moderate) or '4' (severe) per treatment group. Then, in Part B, subjects who were assigned to placebo in the first part of the study will receive the highest dose of ASN002 (i.e. 80 mg) for the rest of the treatment period (up to Week 32). The subjects who were assigned ASN002 in the first part of the study will continue on the same assigned treatment dose during the second part of the study (Week 16 to Week 32). The total treatment period of 32 weeks will be followed by a 4-week follow-up period. For scheduled study visits, subjects will come to the study centers on 13 occasions: screening; Day 1; Weeks 2, 4, 8, 12, 16, 18, 20, 24, 28 and 32 (end of treatment visit); and Week 36 (follow-up visit)/early termination (ET).

[figure not shown]
Efficacy will be assessed using mTLSS, PGA, HECSI, pain VAS and Extent of Disease. In addition, a 6-grade PaGA scale will be used. Quality of life will be evaluated using DLQI. Impact on work productivity and activity will be studied using the WPAI-SHP questionnaire.

Safety will be assessed by collecting AEs, recording vital signs, performing physical examination and 12-lead ECG, and evaluating clinical laboratory tests.

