5.1 Sample Size

Assuming a common standard deviation of 39% for the percent change-from-baseline mTLSS, a difference of 25% and 35% between the 40 mg dose vs. placebo and the 80 mg dose vs. placebo, respectively, alpha of 5% (two-sided), 25 patients per group would insure an 80% power to obtain a statistically significant treatment effect (using the general F test in an analysis of variance). Assuming between 25-30% dropout rates, up to 35 patients per group will be included in this study.

PPD	STATISTICAL ANALYSIS PLAN, Version Final 1.0
Protocol Number: ASN002AD-202 V6.0	Sponsor: Asana BioSciences, LLC

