Overall type 1 error control

PPD	STATISTICAL ANALYSIS PLAN, Version Final 1.0
Protocol Number: ASN002AD-202 V6.0	Sponsor: Asana BioSciences, LLC

For the primary endpoint of percent change-from-baseline in hand mTLSS at Week 16, a Hochberg step-up procedure adjustment will be done to test the two comparisons of interest (40mg vs. Placebo and 80mg vs. Placebo) as detailed in Section 6.5.

Sensitivity Analysis:

Additional sensitivity analyses will be performed for the primary endpoint - percent change from baseline in mTLSS using MMRM model described above and including all efficacy hand mTLSS data for these subjects (before and after the prohibited medication).

Subgroup Analysis:

Subgroup analysis by PGA strata will also be presented for the primary endpoint -percent change from baseline in mTLSS. MMRM model will be used with treatment, visit and treatment-by-visit interaction as fixed effects, and baseline hand mTLSS as a covariate and primary comparison will be performed at Week 16.

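### The PGA 3 and PGA 4 subgroups are tested in models without a treatment-by-PGA term, so no planned analysis estimates whether the effect on mTLSS differs by baseline severity

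*SAP*

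**What the plan says.** SAP 6.6 announces a subgroup analysis of the primary endpoint by PGA 3 and PGA 4, with inferential statistics. The Subgroup Analysis paragraph of SAP 13.1 gives the model: "MMRM model will be used with treatment, visit and treatment-by-visit interaction as fixed effects, and baseline hand mTLSS as a covariate", with the comparison made at Week 16. The PGA term of the primary model is gone and nothing crosses treatment with PGA. The SAP does not say that each stratum gets its own model, but with these terms no other reading makes sense.

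The tests are formal. SAP 5.6 sets two-sided 0.05 as the default. SAP 6.5 calls p-values nominal for secondary endpoints and repeated assessments, and is silent on subgroups. By contrast, the CHE-subtype subgroup in SAP 13.3 is explicitly descriptive.

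Protocol 9.3.2 states: "Additional interaction terms will also be included in supportive statistical models and will be detailed in the SAP". The only interaction in the SAP is treatment-by-visit. SAP 3.5, the list of changes from the protocol, includes the added PGA subgroup analysis but does not mention that these models are absent.

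On size, SAP 3.1 says: "Subjects with moderate CHE will be limited to 30% of total enrollment". The SAP gives no expected subgroup size, subgroup power or rule for interpreting the two results together.

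**The concern.** Two p-values, one per stratum, do not answer the question a subgroup analysis raises. A significant result in one stratum beside a nonsignificant one in the other is not evidence that the effects differ; that needs an estimate of the difference between them. Here the strata are of very unequal size, so the larger one is favored to reach significance whatever the truth.

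People will look at this comparison. Moderate disease was admitted in protocol version 5.0, and PGA became a stratification factor in the same amendment. If the severe stratum is significant and the moderate one is not, it would be easy to conclude that the drug does not work in moderate CHE, and the SAP contains nothing to guard against that.

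**Working it through.** **Inputs.** From SAP 5.1: a planning SD of 39 points for percent change in mTLSS; true effects against placebo of 25 points (40 mg) and 35 points (80 mg); and, on dropout, "Assuming between 25-30% dropout rates, up to 35 patients per group will be included in this study". From SAP 3.1: about 105 subjects, 1:1:1 allocation, 30% cap on moderate CHE.

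**The plan's own figure.** SAP 5.1 claims "alpha of 5% (two-sided), 25 patients per group would insure an 80% power to obtain a statistically significant treatment effect"; the test it has in mind is the overall F test across the three groups. With group means 0, 25 and 35 (mean 20), the noncentrality is 25 × (20² + 5² + 15²) / 39² = 25 × 650 / 1521 = 10.7. On 2 and 72 df, power is 82.5%; 24 per group gives 80.8%. Dropout inflation gives 25/0.75 = 33.3 and 25/0.70 = 35.7, consistent with 35. The overall sizing reproduces and is not in question.

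**Subgroup sizes per arm.**
- PGA 3 at randomization: 0.30 × 105 / 3 = 10.5 at most.
- PGA 3 at Week 16: 10.5 × 0.70 = 7.4 to 10.5 × 0.75 = 7.9. I use 7.5, which is 30% of 25.
- PGA 4 with the cap filled: 24.5 at randomization and 17.5 at Week 16.

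**Precision and power within a stratum.** One dose against placebo, SE = 39 × √(2/n), variance pooled over three arms with 3(n − 1) df, noncentral t power at two-sided 0.05.

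| Stratum | n per arm | SE | 95% half-width | Power, 25 points | Power, 35 points |
|---|---|---|---|---|---|
| PGA 3 | 10.5 | 17.0 | 34.8 | 29% | 51% |
| PGA 3 | 7.5 | 20.1 | 42.1 | 22% | 38% |
| PGA 4 | 24.5 | 11.1 | 22.2 | 60% | 87% |
| PGA 4 | 17.5 | 13.2 | 26.5 | 46% | 74% |

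The SD of 39 is stated for the whole trial; using it in each stratum is an assumption. Half-widths scale directly with it: in PGA 3 they are 34.8/39 = 0.89 to 42.1/39 = 1.08 times whatever the SD is.

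**Chance of discordant results when the true effects are identical.** With p₃ and p₄ the two powers, P(exactly one significant) = p₃(1 − p₄) + p₄(1 − p₃).
- Randomized numbers, 25 points: 0.295 × 0.400 + 0.600 × 0.705 = 0.54.
- Randomized numbers, 35 points: 0.511 × 0.128 + 0.872 × 0.489 = 0.49.
- Week 16 numbers, 25 points: 0.219 × 0.540 + 0.460 × 0.781 = 0.48.
- Week 16 numbers, 35 points: 0.379 × 0.260 + 0.740 × 0.621 = 0.56.

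The second product in each line is the pattern of severe significant and moderate not: 36 to 46% of trials, produced by sample size alone.

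**What an interaction contrast would deliver.** SE = 39 × √(2/n₃ + 2/n₄), normal approximation.
- 10.5 and 24.5 per arm: SE 20.3; half-width 1.96 × 20.3 = 40; difference detectable with 80% power 2.80 × 20.3 = 57 points; power for a 25-point difference between strata 23%.
- 7.5 and 17.5 per arm: SE 24.1; half-width 47; detectable difference 67 points; power 18%.

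**The case against.** The strongest reply is that the remedy learns little more than the plan does. An interaction test with 18 to 23% power for a 25-point difference is no stronger than the within-stratum tests, and a nonsignificant result invites the opposite mistake of declaring the effect uniform. This stands as a limit on the fix. It argues for reporting the interaction as an estimate with its interval, not for leaving two unequal p-values as the only output.

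The calculations also simplify. The lower figures count only subjects with Week 16 data, whereas MMRM uses earlier visits from dropouts and adjusts for baseline. Hence the ranges, with randomized numbers as the favorable end. The 30% is a cap, so the moderate stratum may be smaller still. It is also fair that this is supportive Phase 2 output: error control covers only the two primary dose comparisons, and no decision rule uses the stratum p-values.

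Three stronger readings are tempting, and the documents do not support them:
- *The protocol promised a treatment-by-PGA model.* Protocol 9.3.2 names neither PGA nor any other factor. What can be said is that the deferred terms are neither specified nor declared dropped.
- *The plan makes it impossible to see a difference by severity.* The strata contain different subjects, so their estimates are independent, and a reader could difference them and derive a CI. The gap is that no planned analysis does so.
- *The PGA 3 model will fail to converge.* Five post-baseline visits in Part A give 15 unstructured covariance parameters and 15 treatment-by-visit means from at most about 31 subjects. That is a reason for caution, but those subjects could supply up to 31 × 5 = 155 observations, failure is not shown, and SAP 13.1 has a written covariance fallback.

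**Conclusion.** The concern holds as an improvement worth making, not as a threat to the primary analysis. The SAP tests within PGA strata, plans no estimate of the difference between them, and leaves the protocol's deferred interaction terms unaddressed. Under the SAP's own planning figures the moderate stratum is too small for its p-value to be informative, and discordant stratum results would be expected in roughly half of trials (48 to 56%) with no true difference by severity. These figures rest on a filled 30% cap, even allocation within strata, an SD of 39 in each stratum, and sample sizes between the randomized and Week 16 numbers. The overall sample size, primary model and trial conduct are unaffected.

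**What to change.** In SAP 13.1, add a supportive MMRM on all mITT subjects that extends the primary model with treatment-by-PGA and treatment-by-PGA-by-visit terms, together with the PGA main effect and PGA-by-visit terms these require. Keep the PGA terms in this model whatever is decided about PGA in the primary model. For each dose against placebo, report the Week 16 difference within each stratum and the interaction contrast, all with 95% CIs. Label the stratum results, and any stratum p-values kept, as descriptive in SAP 6.6 and 13.1. State that neither discordant stratum p-values nor a nonsignificant interaction is to be interpreted on its own. In SAP 3.5, list any interaction models deferred by Protocol 9.3.2 that are not restored.

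The cost is SAP wording and one additional model, settled before the Part A lock. The model assumes a common covariance across strata, and its interaction estimate will have a half-width of 40 to 47 points. That width should be stated in advance so that the result is read as an interval and not as a verdict on uniformity.

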13.2 Secondary Endpoints

Hand modified Total Lesion Symptom Score (mTLSS)

mTLSS will also be analyzed as follows:

- Change from baseline in hand mTLSS score at Weeks 4, 8,12 and 16
- Percent change from baseline in hand mTLSS at Weeks 4, 8, 12

Hand Physician Global Assessment (PGA) score

The PGA is a global assessment of the current state of the disease. It is a 5-point scale of overall disease severity by rating the particular signs and symptoms of CHE (erythema, scaling, hyperkeratosis/lichenification, vesiculation, oedema, fissures and pruritus/pain). A detailed description of each PGA severity score is provided in Table 3.

PPD	STATISTICAL ANALYSIS PLAN, Version Final 1.0
Protocol Number: ASN002AD-202 V6.0	Sponsor: Asana BioSciences, LLC

Table 3. Physician's Global Assessment

PGA severity	Features	Intensity	Area involved ^a
Severe (4)	Erythema, scaling, hyperkeratosis/lichenification	At least one moderate or severe	> 30% of affected hand ^b surface
	Vesiculation, oedema, fissures, pruritus/pain	At least one severe	
Moderate (3)	Erythema, scaling, hyperkeratosis/lichenification	At least one mild or moderate	10–30% of affected hand ^b surface
	Vesiculation, oedema, fissures, pruritus/pain	At least one moderate	
Mild (2)	Erythema, scaling, hyperkeratosis/lichenification	At least one mild	Less than 10% of affected hand ^b surface
	Vesiculation, oedema, fissures, pruritus/pain	At least one mild	
Almost clear (1)	Erythema, scaling, hyperkeratosis/lichenification	At least one mild	Less than 10% of affected hand ^b surface
	Vesiculation, oedema, fissures, pruritus/pain	Absent	
Clear (0)	Erythema, scaling, hyperkeratosis/lichenification	Absent	Not detectable
	Vesiculation, oedema, fissures, pruritus/pain	Absent	

^aArea involved does not apply to patients with mostly fingertips eczema. Affected hand surface refers to the surface area of the more severely affected side (palmar or dorsal) of the more affected hand.

^bFor PGA assessment on feet, % of feet surface is to be used.

Hand PGA score will be analyzed as follows:

PPD	STATISTICAL ANALYSIS PLAN, Version Final 1.0
Protocol Number: ASN002AD-202 V6.0	Sponsor: Asana BioSciences, LLC

- Proportion of subjects achieving at least a 2-grade reduction from baseline to clear (0), almost clear (1) or mild (2) in hand PGA at Weeks 4, 8, 12 and 16.
- Proportion of subjects achieving a hand PGA of clear (0) or almost clear (1) at Weeks 4, 8, 12 and 16.
- Change from baseline in hand PGA at Weeks 4, 8, 12 and 16.
- Time to response defined as achieving an assessment of clear (0), or almost clear (1) in hand PGA.

Subgroup analysis by PGA strata at baseline (3 vs 4) will be done on the following endpoints:

- Proportion of subjects achieving a hand PGA of clear (0) or almost clear (1) at Weeks 4, 8, 12 and 16.
- Proportion of subjects achieving at least a 2-grade reduction from baseline to clear (0), almost clear (1) or mild (2) in hand PGA at Weeks 4, 8, 12 and 16.
- Change from baseline in hand PGA at Weeks 4, 8, 12 and 16.

Hand Eczema Severity Index (HECSI)

The HECSI scoring system incorporates both the extent and the intensity of the disease. Each hand will be divided into five areas [fingertips, fingers (except the tips), palms, back of hands and wrists]. For each of these areas the intensity of the six following clinical signs: erythema, induration / papulation, vesicles, fissuring, scaling and oedema will be graded on the following scale: 0, no skin changes; 1, mild disease; 2, moderate and 3, severe. For each location (total of both hands) the affected area will be given a score from 0 to 4 (0, 0%; 1, 1–25%; 2, 26–50%; 3, 51–75% and 4, 76–100%) for the extent of clinical symptoms. Finally, the score given for the extent at each location will be multiplied by the total sum of the intensity of each clinical feature, and the total sum called the HECSI score will be calculated, varying from 0 to a maximum severity score of 360 points. The score will be set to missing in case of at least one missing value.

A detailed description of the HECSI scoring system is shown in

HECSI will be analyzed as follows:

- Change and percent change from baseline in Hand Eczema Severity Index (HECSI) at Weeks 4, 8, 12 and 16.

PPD	STATISTICAL ANALYSIS PLAN, Version Final 1.0
Protocol Number: ASN002AD-202 V6.0	Sponsor: Asana BioSciences, LLC

Table 4.

HECSI will be analyzed as follows:

- Change and percent change from baseline in Hand Eczema Severity Index (HECSI) at Weeks 4, 8, 12 and 16.

Table 4. Hand Eczema Severity Index

Clinical Signs	Fingertips	Fingers (except tips)	Palm of Hands	Back of Hands	Wrists
Erythema (E)					
Infiltration / Papulation (I)					
Vesicles (V)					
Fissures (F)					
Scaling (S)					
Oedema (O)					
SUM (E + I + V + F + S + O)					
Extent (Ex)					
Total HECSI score =	Sum xEx +	Sum xEx +	Sum xEx +	Sum xEx +	Sum xEx
Total HECSI score (min 0; max 360). For each location (total of both hands) the affected area will be given a score from 0 to 4 (0= 0%; 1= 1–25%; 2= 26–50%; 3= 51–75% and 4= 76–100%) for the extent of clinical symptoms. Finally, the score given for the extent for each location will be multiplied by the total sum of the intensity of each clinical feature (each contributing equally to the final score), and the total sum called the HECSI score will be calculated, varying from 0 to a maximum severity score of 360 points.					

Patient Global Assessment (PaGA)

On the day of the visits specified in Table 1, using the PaGA chart, subjects will be asked by the investigator to grade their overall change from baseline in their CHE by selecting one of the following descriptions found in Table 5. Patient Global Assessment^{2,10}

Cleared or Almost Cleared	
Marked improvement (at least 75% clear)	

PPD	STATISTICAL ANALYSIS PLAN, Version Final 1.0
Protocol Number: ASN002AD-202 V6.0	Sponsor: Asana BioSciences, LLC

Moderate improvement (at least 50% clearing)	
Mild improvement (at least 25% clearing)	
No change	
Worsening	

PaGA will be analyzed as follows:

- Actual hand Patient Global Assessment (PaGA) at Weeks 4, 8, 12 and 16.

below, which best matches their perception of treatment effect. Since PaGA was assessed at baseline as well all subjects were asked to grade their baseline visit score as 0 = no change at baseline.

Table 5. Patient Global Assessment^{2,10}

Cleared or Almost Cleared	
Marked improvement (at least 75% clear)	
Moderate improvement (at least 50% clearing)	
Mild improvement (at least 25% clearing)	
No change	
Worsening	

PaGA will be analyzed as follows:

- Actual hand Patient Global Assessment (PaGA) at Weeks 4, 8, 12 and 16.

Dermatology Life Quality Index (DLQI)

PPD	STATISTICAL ANALYSIS PLAN, Version Final 1.0
Protocol Number: ASN002AD-202 V6.0	Sponsor: Asana BioSciences, LLC

Dermatology Life Quality Index Questionnaire (DLQI) is a simple 10-question validated questionnaire that has been used in more than 40 different skin conditions. The DLQI is the most frequently used instrument in studies of randomized controlled trials in dermatology. The DLQI total score is defined as the sum of the 10 item scales, ranging from 0 to 30. If missing answers or mistakes, the following rules will be followed:

1. If one question is left unanswered this is scored 0 and the scores are summed and expressed as usual out of a maximum of 30.
2. If two or more questions are left unanswered the questionnaire is not scored.
3. If question 7 is answered 'yes' this is scored 3 even if in the same question one of the other boxes is ticked.
4. If question 7 is answered 'no' or 'not relevant' but then either 'a lot' or 'a little' is ticked this is then scored 2 or 1. If it is answered 'no', but the second half is left incomplete, the score will remain 0.

DLQI will be analyzed as follows:

- Change from baseline in hand Dermatology Life Quality Index (DLQI) at Weeks 2, 4, 8, 12, and 16.

Pain visual analog scale (VAS)

Pain intensity of the CHE will be recorded at the visits specified in Table 1 using a pain Visual Analog Scale (VAS). Pain intensity will be evaluated by asking subjects to place a line perpendicular to the VAS line at the point that represents their worst pain intensity over the last 24 hours.¹³ The pain VAS, represented in Figure 2 is a scale from 0 to 10, where 0 indicates no pain and 10 indicate the worst imaginable pain.¹³

Figure 2: Pain Visual Analog Scale

Pain VAS will be analyzed as follows:

PPD	STATISTICAL ANALYSIS PLAN, Version Final 1.0
Protocol Number: ASN002AD-202 V6.0	Sponsor: Asana BioSciences, LLC

- Change and percent change from baseline in pain visual analog scale (VAS) at Weeks 4, 8, 12 and 16.

Secondary Endpoint Analyses

The key secondary analysis will be based on the data from Part A with the exception of Time to PGA response analysis. MMRM as described for the primary efficacy analyses (Section 13.1) will be used to analyze the change and/or percent change in hand mTLSS, HECSI, DLQI and pain VAS for weeks 4, 8, 12 and 16 (Part A). Analyses will be based on the mITT population and supported by the PP population.

For categorical efficacy endpoints involving proportions hand PGA, a Cochran Mantel Hansel test (CMH) stratified by baseline PGA will be presented by visit for Part A. Analyses will be based on the mITT population for all secondary parameters and supported by the PP population. Missing data at any post-baseline assessment will be imputed as a non-responder.

Actual values of PaGA will summarized descriptively using frequency and percentage.

Time to response relative to baseline (based on hand PGA) will be compared between treatments using the Kaplan Meier method. A subject will be considered censored if he has not met the event of interest at the end of the study or if the subject is lost to follow up at last observation. Those subjects will be censored at their last available hand PGA assessment.

Descriptive statistics will be presented for all secondary endpoints by visit and treatment group and sorted by Part A.

All endpoints relative Part B for the above assessments are considered exploratory only and will be summarized descriptively by initial treatment group and overall.

